7.2.5.2 Stopping Rules for Delayed AEs During Dose-Escalation

Delayed AEs fulfilling criteria of DLTs (i.e., occurring after the 4-week DLT evaluation period) will be evaluated on a case-by-case basis. Delayed DLTs will not be used to estimate the MTD for dose-escalation. However, if 2 or more delayed DLTs are noted within a dose-escalation cohort, further accrual in that cohort will be held pending safety analysis of the AEs.

7.2.5.3 Safety Stopping Rules in the Expansion Cohorts

Safety Monitoring Committee (SMC) meetings will be held according to the SMC charter to evaluate the safety data in Part A-2 (optional) and Part B. Within Part A-2, the SMC will meet and evaluate the DLT rate and re-consider dosing/dosing intervals whenever a patient experiences a DLT as well as when six patients have completed the 28-day DLT evaluation period for patients dosed at 1400mg flat dose in the optional Part A-2. The SMC will also meet and evaluate the DLT rate within Part B, whenever in a given Part B dose expansion cohort (Part B; expansion cohorts

B1-B4 and B6-B8) two patients have experienced a DLT and when a minimum of 20 patients have been dosed across all Part B expansion cohorts and the DLT evaluation period for all these dose expansion patients has been completed. If the incidence of DLT in Cycle 1 in any Part B cohort is greater than 30%, the SMC may pause enrollment of that or all cohorts and re-assess the dose/regimen of the study drug. For Cohort B5, the SMC will also follow the same DLT evaluation approach for patients enrolled to the combinatorial treatment arm of Cohort B5 as described for Cohort A-2 above: The SMC will meet and evaluate the DLT rate and re-consider dosing/dosing intervals whenever a patient experiences a DLT as well as when six patients have completed the 28-day DLT evaluation period for patients dosed at the 800mg NM21-1480 flat dose in the NM21-1480/PD-1 checkpoint inhibitor arm.

Enrollment into Part B may be held either if the rate of DLTs is $\geq 30\%$ across all the expansion cohorts or if the rate of DLTs is $\geq 30\%$ for a specific expansion cohort with more than 6 patients enrolled. New enrollment should be held in the dose level where a $\geq 30\%$ DLT rate occurs (in such cases, however, lower dose level expansion may continue). Patients who are tolerating a study drug dose level that is being reviewed due to DLTs that occurred in other patients will not be automatically precluded from continued dosing during this safety review, and will be allowed to continue dosing for as long as it is tolerated unless the safety review mandates dose reduction. After safety analysis by the Investigators and the Sponsor, a decision will be made by the SMC whether to resume enrollment into Part B cohorts and continue dosing at the current dose or continue the expansion cohort at a lower NM21-1480 dose. The SMC will also periodically (at least every 6 months, with details described in the SMC charter) review delayed DLTs, while enrollment will be held and/or restarted using the same rules as that for DLTs (i.e., based on a $\geq 30\%$ DLT rate).

For expansion Cohort B5, patients randomized to the NM21-1480/PD-1 checkpoint inhibitor arm will be treated with the 800mg flat dose of NM21-1480. Once 6 patients have been enrolled to the combination treatment arm, enrollment to the cohort will be put on hold until the safety data for the 28-day DLT evaluation period for these six patients have been reviewed by the SMC. At this point, the SMC will determine whether the 800mg NM21-1480 represents a tolerable dose in the combinatorial setting applied in Cohort B5, following the below guiding BOIN principles provided in [Table 10-2](#):

- The 800mg dose level is considered a tolerable dose and technically not considered to represent the MTD in this combinatorial setting because BOIN would recommend further dose escalation at this point (i.e. $\phi \leq 0.236$)
- The 800mg dose level is considered a tolerable dose and to represent the MTD in this combinatorial setting if $\phi > 0.236$ and $\phi \leq 0.3$
- The 800mg dose level is not considered a tolerable dose (i.e. $\phi > 0.3$)

However, the SMC is free to apply a more stringent definition of the MTD for ruling of the 800mg dose level of NM21-1480 in the combinatorial setting applied in Cohort B5 if deemed necessary. Should the SMC, upon review of the 28-day safety data for the first six patients enrolled to the combinatorial arm of Cohort B5 conclude that the 800mg dose is not considered tolerable in this setting, Cohort B5 will be stopped. However, if the SMC concludes at this point that the 800mg dose of NM21-1480 represents a tolerable dose, enrollment into Cohort B5 may be resumed.

Following SMC review of the 28-day safety data for the first six patients enrolled to the combinatorial arm of Cohort B5, the same safety stopping rules will apply as described for Cohorts B1-B4 and B6-B8 above.

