To further characterize the safety and clinical activity of NM21-1480, Part B, Cohorts B1-B4 and B6-B8 will employ a Bayesian Optimal Phase II (BOP2) design to enroll patients with selected advanced solid tumors with locally advanced or metastatic, non-resectable disease, which has progressed despite treatment with standard first-line, or first- *and* second-line, a maximum of 3 previous cytotoxic treatment regimens, or a defined set of previous standard-of-care therapies for Cohorts B1-B4 and B6-B8, as described per specific cohort. Based on the results of Part A of the study and as per SMC recommendation, patients in these cohorts will be dosed at the 800mg flat dose level, considered the presumptive RP2D of NM21-1480, applying a biweekly dosing interval. Cohort B5 will be a randomized, open-label, active-control, Bayesian study cohort in which the combination of NM21-1480 plus standard-of-care anti-PD1 therapy will be compared to standard-of-care anti-PD1 monotherapy in patients with head and neck squamous cell cancer. For Cohort B5, patients randomized to the NM21-1480/PD1 checkpoint inhibitor arm will be treated with 800mg NM21-1480, administered in a biweekly dosing interval. However, a safety run-in for this dose in Cohort B5 will be applied: an enrollment stop will be made once 6 patients have been enrolled to the NM21-1480 plus standard of care arm with remaining patients only to be enrolled once the SMC has reviewed the 28-day safety data for all these 6 patients in comparison to the anti-PD1 treatment arm and has confirmed the tolerability of the 800mg dose in this combination therapy setting. If the 800mg dose of NM21-1480 was not considered to represent a tolerable dose in this combination setting as per SMC decision, the Sponsor may either stop Cohort B5 or together with the SMC or select a lower dose level for continued exploration within Cohort B5. In this latter case a safety run-in with 6 patients would be applied again at such lower dose before remaining patients were to be enrolled to the combination therapy arm. Once an MTD for NM21-1480 in this Cohort B5 combination setting has been determined by the SMC, remaining patients may only be assigned to NM21-1480 dose levels at or below this combination therapy MTD for NM21-1480.

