Part A of the study was formally completed on 23 May 2022 at which occasion, based on availability of at least 28-day safety data for all 25 patients evaluable for BOIN in Part A, the SMC determined that Part A did not technically identify a MTD and that even the highest dose level assessed in Part A (800mg flat dose) was considered a tolerated dose. However, based on the finding that some patients dosed at 24-240mg in Part A developed treatment-emergent ADAs leading to loss of exposure, while this was not observed at the 800mg dose level, a decision was taken to explore one higher dose level (1400mg flat dose) in up to 10 patients within Part A-2 in parallel to studying the 800mg dose level in Part B. For safety evaluation of this single additional dose level, the target toxicity rate applied for BOIN in Part A ($\phi = 0.3$) will be applied. Initially, 6 patients will be dosed with 1400mg of NM21-1480 in Part A-2 and upon completion of the 28-day DLT evaluation period for these six patients, as per SMC call, an additional up to 4 patients may be enrolled at this dose level (to end up with a maximum of 10 patients to be exposed to 1400mg in Part A-2), applying the decision rules defined for BOIN as detailed in Table 10-2. Whenever after 6 patients have completed the 28-day DLT evaluation period at the 1400mg dose level, according to the BOIN decision rules, de-escalation from the 1400mg dose or elimination of

the 1400mg dose would be required, further enrollment into the dose level will be stopped. In such situation, ongoing patients who are tolerating the dose level may be continued at 1400mg flat dose unless the safety review mandates dose reduction in which case the dose may be reduced to 800mg or the patient may be discontinued from treatment based on discussion between the investigator and the Medical Monitor. If tolerability of the 1400mg dose allows for completion of the 28-day DLT evaluation period for 6-10 patients, the SMC will determine based on the BOIN decision rule guidance provided in Table 10-2 whether:

- The 1400mg dose level is considered a tolerable dose and technically not considered to represent the MTD because BOIN would recommend further dose escalation at this point (i.e. $\phi \leq 0.236$)
- The 1400mg dose level is considered a tolerable dose and to represent the MTD if $\phi > 0.236$ and $\phi \leq 0.3$
- The 1400mg dose level is not considered a tolerable dose (i.e. $\phi > 0.3$)

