 - e) If none of the actions (i.e., escalation, de-escalation or elimination) is triggered, treat the new patients at the current dose.
 - f) If the current dose is the lowest dose and the rule indicates dose de-escalation, treat the new patients at the lowest dose unless the number of DLTs reaches the elimination boundary, at which point terminate the study for safety.
 - g) If the current dose is the highest dose and the rule indicates dose-escalation, treat the new patients at the highest dose.
- h) Repeat step 2 until the maximum sample size of 25 is reached or stop Part A of the study if the number of patients treated at the current dose reaches 12.

Figure 10–1 BOIN Design

* DLT rate =
$$\frac{\text{Total number of patients who experienced DLT at the current dose}}{\text{Total number of patients treated at the current dose}}$$

Abbreviations: DLT = Dose-limiting toxicity; MTD = Maximal tolerated dose

After the study is completed, the MTD based on isotonic regression as specified in [Liu and Yuan, 2015](#) is selected (the MTD for which the isotonic estimate of the toxicity rate is closest to the target toxicity rate. If there are ties, the higher dose level is selected when the isotonic estimate is lower than the target toxicity rate and the lower dose level is selected when the isotonic estimate is greater than or equal to the target toxicity rate). [Table 10-2](#) below provides the decision rules to be utilized during the dose-escalation period.

Table 10-2 Dose-Escalation/De-Escalation Decision Rules for the BOIN Design

Actions	The number of patients treated at the current dose											
	1	2	3	4	5	6	7	8	9	10	11	12
Escalate if number of DLT ≤ 0.236	0	0	0	0	1	1	1	1	2	2	2	2
De-escalate if number of DLT ≥ 0.359	1	1	2	2	2	3	3	3	4	4	4	5
Eliminate if number of DLT	NA	NA	3	3	4	4	5	5	5	6	6	7

Abbreviations: BOIN = Bayesian optimal interval; DLT = Dose-limiting toxicity; NA = Not applicable

As of October 29, 2021, 13 evaluable patients have been treated at DL1 to DL5, as shown in [Table 10-3](#) below. PK and PD data show that DL5 has reached the range of therapeutically effective dose. To reduce the chance of exposing patients to higher doses that may yield no additional benefit, amendment is made in Protocol V6.0 to remove DL8 from dose escalation. Accordingly, the maximum sample size in the BOIN is adjusted from 27 to 25.

Table 10-3 Observed Data as of October 29, 2021.

Dose level (DL)	DL1	DL2	DL3	DL4	DL5	DL6	DL7	DL8

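### Cohort B5 run-in: 2 DLTs in 6 patients stops the cohort under the Section 7.2.5.3 text but triggers no action in Table 10-2, which that text cites

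*Protocol*

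**What the plan says.** **Cohort B5 (Protocol 7.2.5.3).** Enrolment pauses once six patients are in the combination arm. The SMC then classifies 800 mg on 28-day DLT data, "following the below guiding BOIN principles provided in" Table 10-2. Three categories are printed:

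- rate at most 0.236: tolerable and not the MTD;
- rate above 0.236 and up to 0.3: tolerable and the MTD;
- rate above 0.3: "The 800mg dose level is not considered a tolerable dose".

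Should the SMC "conclude that the 800mg dose is not considered tolerable in this setting, Cohort B5 will be stopped".

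**Table 10-2 (Protocol 10.3.1).** The de-escalation row is labelled "De-escalate if number of DLT ≥ 0.359". For six patients the table escalates at 1 or fewer DLTs, de-escalates at 3 or more and eliminates at 4 or more. The accompanying notes add: "If none of the actions (i.e., escalation, de-escalation or elimination) is triggered, treat the new patients at the current dose".

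**Part A-2 at 1400 mg (Protocol 7.2.5).** After six patients, up to four more may enter, "applying the decision rules defined for BOIN as detailed in Table 10-2". Enrolment stops if BOIN would require de-escalation or elimination. The same three categories then label the dose, the last being "The 1400mg dose level is not considered a tolerable dose" for a rate above 0.3.

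**Synopsis, Part B.** If 800 mg fails in the combination, "the Sponsor may either stop Cohort B5 or together with the SMC or select a lower dose level for continued exploration", with a fresh six-patient run-in at that lower dose.

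**The concern.** The text presents its cut-offs as those of Table 10-2, but its upper cut-off is 0.3 and the table's is 0.359. A result between the two is handled differently depending on which place the SMC reads, and with six patients 2/6 is such a result. This is a patient-safety stopping rule, so the same data should lead to one action.

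Three related points:

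- Determining the combination MTD is a stated B5 objective, yet the category that would declare 800 mg the MTD may be unreachable with six patients.
- The consequence of failure differs between the synopsis (stop, or try a lower dose) and Section 7.2.5.3 (stop).
- Within Section 7.2.5.3, the general Part B trigger is first a DLT rate above 30% and then a rate of 30% or more.

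**Working it through.** **Inputs.** Target rate 0.3, boundaries 0.236 and 0.359, elimination when Pr(p > 0.3 | data) > 0.95, and Table 10-2 (Protocol 10.3.1). Run-in size 6 and text cut-offs 0.236 and 0.3 (Protocol 7.2.5.3). The protocol does not state the remaining BOIN settings. I assumed the usual φ1 = 0.6φ = 0.18 and φ2 = 1.4φ = 0.42, with a Beta(1,1) prior for elimination.

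**Step 1: reproduce Table 10-2.**

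- λe = ln[(1−φ1)/(1−φ)] / ln[φ(1−φ1)/(φ1(1−φ))] = ln(0.82/0.70) / ln(0.246/0.126) = 0.2365
- λd = ln[(1−φ)/(1−φ2)] / ln[φ2(1−φ)/(φ(1−φ2))] = ln(0.70/0.58) / ln(0.294/0.174) = 0.3585

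At n = 6, escalate at floor(6 × 0.2365) = 1 or fewer and de-escalate at ceil(6 × 0.3585) = 3 or more. Pr(p > 0.3 | data) is 0.874 at 3 DLTs and 0.971 at 4, so elimination starts at 4. All three rows of the table reproduce for n = 1 to 12. The table is internally sound.

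**Step 2: map each B5 result under both rules.**

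| DLTs of 6 | Rate | Text, 7.2.5.3 | Table 10-2 |
|---|---|---|---|
| 0 | 0.000 | tolerable, not MTD | escalate |
| 1 | 0.167 | tolerable, not MTD | escalate |
| 2 | 0.333 | **not tolerable, stop B5** | **no action, stay at dose** |
| 3 | 0.500 | not tolerable, stop B5 | de-escalate |
| 4 to 6 | 0.667 or more | not tolerable, stop B5 | eliminate |

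At 2/6, Pr(p > 0.3 | data) = 0.647, well short of the 0.95 elimination limit. No count out of 6 lies above 0.236 and at or below 0.3 (1/6 = 0.167, 2/6 = 0.333), so the tolerable-and-MTD category is empty at this review.

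**Step 3: how often the conflict would arise.** With X ~ Binomial(6, p) and p assumed:

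| True DLT rate p | P(X = 2), the conflict | P(X ≥ 2), not tolerable (text) | P(X ≥ 3), de-escalate or eliminate (table) |
|---|---|---|---|
| 0.05 | 3.1% | 3.3% | 0.2% |
| 0.10 | 9.8% | 11.4% | 1.6% |
| 0.20 | 24.6% | 34.5% | 9.9% |
| 0.30 | 32.4% | 58.0% | 25.6% |
| 0.40 | 31.1% | 76.7% | 45.6% |

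Two DLTs is the single most likely count only when 15p > 6(1−p) and 15(1−p) > 20p, that is for p between 0.286 and 0.429. Below that range, one or no DLT is more likely.

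**Step 4: Part A-2.** For n = 6 to 10 there are 7 + 8 + 9 + 10 + 11 = 45 possible DLT counts. The labels and the table disagree at two of them: 2/6 and 3/9 (both 0.333, with de-escalation starting at 3 and 4 respectively). There, enrolment at 1400 mg may continue while the label reads not tolerable. They agree at 2/7 (0.286), 2/8 (0.25) and 3/10 (0.30).

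**Step 5: the 30% triggers.** The two general Part B wordings differ only at exactly 30%, such as 3 of 10, and much of that wording is permissive.

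**The case against.** The strongest reply is that the B5 text is self-sufficient. It prints its own cut-offs and calls the BOIN principles guiding. The 0.3 limit also matches the protocol's MTD definition (DLTs in at most 30% of patients, Section 7.1). The stay-at-dose instruction is a Part A dose-assignment step, and in Part A the MTD is chosen afterwards by isotonic regression. Enrolment is already on hold at six patients, and in B5 it resumes only if the SMC finds the dose tolerable. The SMC may also apply a stricter MTD definition. In Part A-2 the table can be read as governing entry of further patients, with the labels applied later.

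Much of this is fair. An SMC reading only the B5 text gets one answer, the hold limits the danger, and the two-stage reading of Part A-2 leaves a problem only if labelling happens at exactly 2/6 or 3/9. But the text still attributes its rule to a table with a different upper boundary and imports that table unmodified. The stricter-definition clause does not say what the default is at 2/6.

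The size can also be challenged. Table 10-5 shows 0 DLTs in 9 patients at 800 mg and 1 in 25 across Part A. Those are monotherapy data and do not fix the combination rate, but they give no support for the rows at 0.30 and 0.40. At 0.05 to 0.10 the conflict would occur in about 3% to 10% of run-ins.

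**Conclusion.** The inconsistency is real. For B5, exactly one of the seven possible results (2 of 6) means stop in Section 7.2.5.3 and continue at the same dose in Table 10-2. The probability of that result depends on an assumed true rate: 3.1% at 0.05, 24.6% at 0.20 and 32.4% at 0.30. The tolerable-and-MTD category cannot be reached at n = 6. Part A-2 has the same mismatch at 2 of 45 counts. The synopsis and Section 7.2.5.3 disagree about what follows a failed run-in, whichever cut-off is used. The 30% wording difference is minor.

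No enrolled patient was affected. SAP Section 6 reports no patients in B5 and five in A-2, so neither six-patient review was reached. What remains at stake is the protocol of record and any later re-use of these rules. It should be fixed because it concerns a safety stop and costs little. No view is taken here on which boundary or consequence is right.

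**What to change.** Reconcile these places:

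- the B5 categories and stopping sentence in Section 7.2.5.3, and the 1400 mg categories in Section 7.2.5, with Table 10-2;
- the synopsis with Section 7.2.5.3 on what happens if 800 mg fails in B5;
- the two 30% triggers within Section 7.2.5.3.

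The clearest form is a short table giving one action per DLT count, for n = 6 in B5 and n = 6 to 10 in Part A-2, under whichever boundary the sponsor and SMC adopt. Use a symbol other than φ for the observed rate, since Sections 7.2.5 and 10.3.1 define φ as the fixed target of 0.3.

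The cost is protocol and SMC-charter wording. If the protocol will not be amended again, one sentence in the clinical study report is enough, saying that neither six-patient review was reached and the conflicting rules were never applied.

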7.2.5.4 Stopping Rules for Futility in the Expansion Cohorts

A BOP2 design is applied for Part B, Cohorts B1 through B4, and B6 through B8 which includes an interim futility analysis conducted after 25 patients have been enrolled and treated in the respective cohort(s). This futility analysis will be conducted based on availability of response data following completion of the first 2 RECIST 1.1 and iRECIST assessments (i.e., when 12 weeks of imaging data is available) for the 25 patients. The Sponsor in consultation with the SMC will determine at this point whether the cohort shall be stopped or continued. Go/no-go criteria based on posterior probability will be applied as specified in [Table 10-6](#). For Cohort B8, the Sponsor will hold enrollment to the Cohort after 25 patients have received at least one dose of NM21-1480 treatment until all relevant safety, efficacy, PK, immunogenicity and most prominently all relevant PD data that has accrued until then has been reviewed by the Sponsor and the SMC. After this interim review, the Sponsor may decide to stop the cohort, to continue with full enrollment of the cohort or revise eligibility criteria before the remaining 15 patients in the cohort are enrolled.

The go/no-go criteria of the BOP2 are non-binding though, in particular as an ORR of 10% in the patient population assessed may already be considered a clinically meaningful result by the Sponsor e.g., based on clinical subgroup and/or biomarker data. Futility analyses will be done based on availability of 12 weeks data. The data monitoring committee (DMC), consisting of Sponsor representatives will determine whether a cohort shall be stopped or continued after the interim analysis.

In case (a) cohort is not stopped for futility after the interim analysis, enrollment continues until 40 patients per cohort have been enrolled and treated. A final analysis will then be conducted after initial response data (i.e., based on availability of 12-week data) for the total (maximum) of 40 patients for a given cohort is available. Part A study data discussed with SMC on 23 May 2022 demonstrated the development of treatment-emergent anti-drug-antibodies (ADAs) in a relevant fraction of patients dosed at 24mg-240mg. These ADAs were typically associated with rapid elimination of NM21-1480 from the circulation and loss of exposure. However, PK, PD, receptor occupancy and clinical activity data available for the 800mg dose level indicated that at this dose, the issue of loss of exposure was no longer present while full pharmacodynamic activity was

maintained, a phenomenon described for other checkpoint inhibitors (i.e. atezolizumab) at higher doses as well. As such, the SMC agreed with the Sponsor to further study the 800mg dose level as the presumptive RP2D, applying a biweekly dosing interval in Part B of the study.

For Cohort B5, an interim analysis will be performed after a minimum of 60 patients have been enrolled. At this point recruitment will be paused, the accumulated data analysed and regulatory authorities consulted. At the interim analysis the cohort will be regarded as futile (non-binding) if the probability of observing a difference in estimated effects between control and treatment of at least 15% is less than 0.1. However, as with the other cohorts, decisions at the interim point will be taken based on clinical and regulatory input and not formal statistical testing.

7.2.6 Withdrawal of Participants

Participants may voluntarily withdraw consent to participate in the study for any reason at any time or may be withdrawn at the discretion of the Investigator for safety, behavioral, compliance, or administrative reasons.

Withdrawal of consent occurs when a participant does not want to participate in the study anymore and does not want to attend any further visits or assessments, have further study-related contact, or allow analysis of already obtained biologic material. If a participant withdraws from the study, they may request destruction of any samples taken and not tested, and the Investigator must document this in the site study records. If the participant withdraws consent for disclosure of future information, the Sponsor may retain and continue to use any data collected before such withdrawal of consent.

If a patient is withdrawn from the study (during the Treatment or Follow-up period), all evaluations associated with that study visit should be performed and the date and reason for study discontinuation should be documented on the electronic case report form (eCRF). For patients that are withdrawn while in the treatment period for reasons other than disease progression, every effort should be made to continue monitoring their disease status by radiologic imaging at FU2 or FU3 or until (1) the start of new anticancer treatment, (2) disease progression, (3) death, or (4) the end of the study, whichever occurs first. If a participant withdraws consent, the Investigator must make every effort to determine the primary reason for this decision, should obtain written notice of the decision from the patient, if possible, should document the decision in source and additionally record this information on the treatment disposition eCRF page. If the participant decides to completely withdraw from the study (refuses any further study participation or contact), all study participation for that participant will cease and data to be collected at subsequent visits will be considered missing. Investigational treatments must be discontinued and no further assessments conducted. Further attempts to contact the participant are not allowed unless safety findings require communication or follow-up.

However, for safety reasons, visit should be conducted as far as possible if the withdrawn participant is willing to undergo the assessments.

The Investigator must also contact the interactive web response system service to register the participant's discontinuation from investigational treatment.

